2. LIST OF ABBREVIATIONS

Term	Definition / description
ADS	Analysis data set
AE	Adverse event
ALT	Alanine transaminase
AST	Aspartate aminotransferase
ATC	Anatomical Therapeutic Chemical
AUC _{0-∞}	Area under the concentration-time curve of the analyte in plasma over the time interval from 0 extrapolated to infinity
AUC _{0-tz}	Area under the concentration-time curve of the analyte in plasma over the time interval from 0 to the last measured time point
AUC _{τ,ss}	Area under the concentration-time curve of the analyte in plasma over a dosing interval
BI	Boehringer Ingelheim
bid	Bis in die (twice daily dosing)
RPM	Report planning meeting
BSA	Body surface area
C _{max}	Maximum measured concentration of the analyte in plasma
C _{max,ss}	Maximum measured concentration of the analyte in plasma at steady state
CRF	Case Report Form
CT	Concomitant therapy
CTP	Clinical Trial Protocol
CTR	Clinical Trial Report
CV	Coefficient of variation
DBL(M)	Data Base Lock (Meeting)
DLCO	Diffusing capacity of the Lung for Carbon monoxide
ECG	Electrocardiogram
EMA	European Medicines Agency
EoT	End-of-Text
FU	Follow-up
gCV	Geometric coefficient of variation
gMean	Geometric mean

Term	Definition / description
ICH	International Conference on Harmonisation
IPF	Idiopathic Pulmonary Fibrosis
(I)PV	(Important) Protocol violation
Max	Maximum
MedDRA	Medical Dictionary for Regulatory Activities
Min	Minimum
MQRM	Medical Quality Review Meeting
NA	Not applicable
PK	Pharmacokinetics
PKS	Pharmacokinetic analysis set
PN	Preferred Name
PT	Preferred term
qd	Quaque die (everyday)
RNA	Ribonucleic acid
SAS	Statistical analyses software
SD	Standard deviation
SOC	System organ class
SSC	Special Search Categories
tid	Ter in die (3 times a day)
TS	Treated set
TSAP	Trial statistical analysis plan
ULN	Upper limit of normal

3. INTRODUCTION

As per [ICH E9](#), the purpose of this document is to provide a more technical and detailed elaboration of the principal features of the analysis described in the protocol, and to include detailed procedures for executing the statistical analysis of the primary and secondary variables and other data.

This TSAP assumes familiarity with the Clinical Trial Protocol (CTP), including Protocol Amendments. In particular, the TSAP is based on the planned analysis specification as written in CTP Section 7 “Statistical Methods and Determination of Sample Size”. Therefore, TSAP readers may consult the CTP for more background information on the study, e.g., on study objectives, study design and population, treatments, definition of measurements and variables, planning of sample size.

SAS[®] Version 9.4 or later version will be used for all analyses.

Pharmacokinetic (PK) parameters will be calculated using WinNonlin[™] software (professional Network version 6.3, Pharsight Corporation, Mountain View, CA 94041-1530, USA).

4. CHANGES IN THE PLANNED ANALYSIS OF THE STUDY

All analyses described in this TSAP are in accordance with the statistical methods described in the CTP.

5. ENDPOINTS

5.1 PRIMARY ENDPOINTS

The primary endpoints will be used as defined in Section 5.1.1 of the CTP as pharmacokinetic endpoints:

- Group 1
 - AUC_{0-tz} area under the concentration-time curve of **nintedanib** in plasma over the time interval from 0 to the last measured time point (quantifiable concentration)
 - C_{max} maximum measured concentration of **nintedanib** in plasma after single dose administration
- Group 2
 - $AUC_{\tau,ss}$ area under the concentration-time curve of **pirfenidone** in plasma over a dosing interval
 - $C_{max,ss}$ maximum measured concentration of **pirfenidone** in plasma at steady state

5.2 SECONDARY ENDPOINTS

5.2.1 Key secondary endpoints

This section is not applicable as no key secondary endpoint has been specified in the protocol.

5.2.2 Secondary endpoints

Secondary endpoints will be used as defined in Section 5.1.2 of the CTP as pharmacokinetic endpoints:

- Group 1
 - $AUC_{0-\infty}$ area under the concentration-time curve of **nintedanib** in plasma over the time interval from 0 extrapolated to infinity

5.3 FURTHER ENDPOINTS

5.4 OTHER VARIABLES

5.4.1 Demographics and other baseline characteristics

Demographics and other baseline characteristics will include the following. Baseline is defined in [Section 6.7](#).

5.4.1.1 Demographic data

- Gender
- Ethnicity
- Race
- Age [years] will be calculated as : integer part of [(date of informed consent - date of birth) / 365.25]
- Age by category [years] (<65; ≥65-<75; ≥75 and <65; ≥65-<75; ≥75-<85; ≥85)
- Weight [kg] as continuous variable and by category (<30; ≥30 - <60; ≥60 - <90; ≥90)
- Height [cm]
- Body mass index [kg/m²]: Weight[kg] / Height [m]*Height[m], as continuous variable and by category (< 18.5; ≥18.5-<25; ≥25-<30, ≥30)
- Body surface area [m²] (according to Dubois Formula : BSA = 0.007184 * Height[cm]0.725 * Weight[kg]0.425), as continuous variable and by category (<1.73; ≥1.73)

5.4.1.2 Trial indication

- Time elapsed since the first diagnosis of IPF [years] will be calculated as : (date of entry – date of first diagnosis)/365.25
- Time elapsed since the first diagnosis of IPF coded by category (≤ 1 year; > 1 year to ≤ 3 years; > 3 years to ≤ 5 years; > 5 years)

5.4.1.3 Smoking status

- Smoking history (never smoked, ex-smoker, currently smokes)

5.4.1.4 Other baseline characteristics

- Diffusing capacity of the Lung for Carbon monoxide (DLCO) [% predicted] corrected for haemoglobin by the site

5.4.2 Treatment exposure

Treatment exposure will be calculated separately for nintedanib and for pirfenidone.

Time on drug [days] = date of last administration – date of first administration +1 day

Time on actual drug (150 mg bid for nintedanib; 267 or 534 or 801 mg tid for pirfenidone) [days]: sum of time on-treatment for each dose effectively taken

For group 1, time on drug for pirfenidone whatever the dose is will be displayed.

For group 2, time on drug for nintedanib 150 mg bid will be displayed as well as time on drug for pirfenidone whatever the dose is.

Total dose [mg]: Time on actual drug [days] * actual dose [mg]

For pirfenidone, dose reductions are defined as decreases to either 2*267mg tid or 1*267mg tid.

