- 4. Patient will be dispensed two wallets of pirfenidone at Visit 2 and take the full dose (801 mg tid) for 7 consecutive days (Day 1 to Day 7) and then return to the clinic for Visit 3a (Day 8). At Visit 3a they will be dispensed one wallet of pirfenidone and one bottle of nintedanib and be given the remaining wallet of pirfenidone that was dispensed at the previous visit. The will take nintedanib 150mg bid and pirfenidone 801mg tid (or 534mg tid) from Day 9 to Day 15 and then come in to the clinic at Day 16 where they will receive only the morning dose of each drug. (See Section 4.1.4).
- 5. Patients will be supplied with a diary and a dosing card and they will be asked to document the number of capsules they have taken each day and also to record any adverse events during this period.
- 6. Please see separate PK flowchart Group 2 for details during the PK evaluation period Section 10.2.
- 7.
- 8. Urine dipstick pregnancy tests will be provided by central lab and should be performed in all women of childbearing potential.
- 9. If a patient withdraws from the PK evaluation period then the patient should be managed according to Figure 4.1.4:1.
- 10. The patient will stop all trial medication on Day 16 (except for the doses given at clinic) and have a washout period from study drug until the PK FU visit.
- 11. Spirometry should be conducted using local standard equipment.
- 12. During the PK evaluation period the patient must have seven consecutive days of both nintedanib 150mg bid and pirfenidone 801mg tid (or 534mg tid) before they should have the PK day on Visit 3b.
- 13.
- 14. At Visit 4 (PK FU) optional nintedanib Named Patient Programme will be discussed with the patient
- 15. AEs and concomitant therapy should be checked at regular intervals during the PK days.
- 16. The PK Follow Up visit should occur at least 28 days after last drug intake.
- 17. DLCO testing will be performed once at visit 1 or 2, or during the screening period (visit 1 to visit 2). The results will be corrected for haemoglobin by the site, see section 10.3 for further details..

Page 10 of 118

Proprietary confidential information © 2016 Boehringer Ingelheim International GmbH or one or more of its affiliated companies

TABLE OF CONTENTS

CLINICA	L TRIAL PROTOCOL	1
TITLE PA	GE	1
CLINICA	L TRIAL PROTOCOL SYNOPSIS	2
FLOW CH	IART - GROUP 1	6
FOOTNO	ГЕS – GROUP 1	7
FLOW CH	IART - GROUP 2	8
FOOTNO	ΓΕS – GROUP 2	9
TABLE O	F CONTENTS1	0
ABBREVI	ATIONS1	4
1.	INTRODUCTION1	6

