4.1 TREATMENTS TO BE ADMINISTERED

4.1.1 Identity of BI investigational product(s) and comparator product(s)

Table 4.1.1: 1 Nintedanib (investigational drug)

Substance:	Nintedanib
Pharmaceutical formulation:	Soft gelatine capsule
Source:	BI Pharma GmBH & Co. KG
Unit Strength:	150 mg
Posology:	Group 1: Day 1 and Day 23: one 150 mg capsule in the morning
	Group 2: Days 9-15: one 150 mg capsule in the morning and one in the evening
	Day 16: one 150 mg capsule in the morning
Route of administration:	Oral (swallowed) administration with food

Table 4.1.1: 2 Pirfenidone (investigational drug)

Substance:	Pirfenidone
Pharmaceutical formulation:	Capsule
Source:	Roche Registration Limited (previously InterMune
	UK Ltd)
Unit Strength:	267 mg
Posology:	Group 1 Days 2-8: one capsule three times a day Days 9-15: two capsules three times a day Days 16-23: three capsules three times a day
	Group 2 Days 1-15: three capsules three times a day Day 16: three capsules in the morning only
Route of administration:	Oral (swallowed) administration with food

sion 4.0 Page 33 of 118

Proprietary confidential information © 2016 Boehringer Ingelheim International GmbH or one or more of its affiliated companies

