5.4.3 Treatment compliance

Compliance for nintedanib (group 2 only) and compliance for pirfenidone will be calculated separately over the study as:

$$\text{Compliance [\%]} = \frac{\text{Number of capsules actually taken over the period}}{\text{Number of capsules which should have been taken over the period}} \times 100$$

The number of capsules which should have been taken over the period will be calculated as:

Number of capsules which should have been taken over the period [capsules] = (date of last administration – date of first administration + 1) [days] × (number of capsules which should be taken per day) ^[1]

^[1] The time of first/ last administration are taken into account, so fewer capsules may be expected to be taken on some days.

For nintedanib, the number of capsules which should be taken per day at dose 150 mg qd is 1. The number of capsules which should be taken per day at dose 150 mg bid is 2.

For pirfenidone, the number of capsules which should be taken per day is 3 at dose 267 mg tid, 6 at dose 534 mg tid, and 9 at dose 801 mg tid.

Only treatment interruptions not due to AE will be considered a compliance issue and will be taken into account in the calculation (duration of interruptions due to AE will be subtracted from the duration of the study period).

Compliance will be categorised as follow: <50%, >=50% to <80%, >=80% to <= 120%, > 120%.

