6. GENERAL ANALYSIS DEFINITIONS

6.1 TREATMENTS

For treatment specifications, see Section 4 of CTP.

The following trial periods will be defined: screening, post-entry, treatment period, off-treatment, Residual Effect Period, follow-up and post-study as follows:

Note: the last day of each of the following periods is excluded.

- **Screening:** from informed consent to date of entry
- **Post-entry** (if applicable): from entry to first trial drug intake.
- **Treatment period:** from first trial drug intake (or re-start of treatment if interruption) to last trial drug intake (or the day before start date of interruption, if interruption) plus one day
- **Off-treatment** (if applicable): from start date of interruption to re-start of treatment
- **Residual Effect Period:** from the last trial drug intake plus one day to last trial drug intake plus 28 days plus one day.
- **Follow-up** (if applicable): from last trial drug intake plus 29 days up to the beginning of post-study period. This period is only created if last trial drug intake took place more than 28 days before trial completion (i.e. date of the follow-up visit or date where the patient discontinued prematurely the trial).
- **Post-study:** from the latest of last trial drug intake plus 29 days or date of trial completion plus 1 day to database lock

For safety analyses, data up to 28 days after last trial drug intake (inclusive) will be considered on-treatment.

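### The total-dose formula in SAP 5.4.2 has no part-day correction, so read literally it overstates exposure for Group 2 completers, whose last day is a morning dose only

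*SAP*

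**What the plan says.** SAP 5.4.2 gives the rule "Total dose [mg]: Time on actual drug [days] * actual dose [mg". The time component is the "sum of time on-treatment for each dose effectively taken", and the levels it covers are listed as "Time on actual drug (150 mg bid for nintedanib; 267 or 534 or 801 mg tid for pirfenidone) [days" (unit: days). No single-intake level is listed for either drug. The same section computes time on drug as last date minus first date plus one. SAP 6.1 runs the treatment period "to last trial drug intake (or the day before start date of interruption, if interruption) plus one day" with the end day excluded, so the day of last intake counts as a whole treatment day. SAP 6.1 also sets interruptions apart as an off-treatment period, "from start date of interruption to re-start of treatment".

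For Group 2, the nintedanib posology in Protocol 4.1.1 is "Days 9-15: one 150 mg capsule in the morning and one in the evening", followed by one morning capsule on Day 16. Pirfenidone is three capsules three times a day on Days 1 to 15 and three capsules in the morning on Day 16. Footnote 4 of the Group 2 flow chart says that at the Day 16 visit "they will receive only the morning dose of each drug".

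SAP 5.4.3 handles part-days for compliance: its footnote takes the times of first and last administration into account, "so fewer capsules may be expected to be taken on some days". It also names a once-daily 150 mg nintedanib level. Neither feature is carried into 5.4.2. SAP 7.7 tabulates total dose of both drugs on the treated set.

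**The concern.** Every Group 2 patient who completes the schedule ends on a part-day. A rule that multiplies whole days by a bid or tid dose credits that day with one nintedanib and two pirfenidone doses that the protocol does not give. The SAP recognises part-days in the neighbouring section, so the two derivations rest on different capsule expectations for the same patient. An intake missed on an otherwise treated day also stays in the total, because nothing in 5.4.2 subtracts it.

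At stake is the accuracy of the total-dose columns in the exposure tables, which a reader would take as the amount of drug received.

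**Working it through.** The documents state no total dose, so there is no figure to reproduce beyond the daily doses, which check: 3 × 3 × 267 = 2403 mg pirfenidone and 2 × 150 = 300 mg nintedanib.

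**Inputs.** Schedule from Protocol 4.1.1 and the Group 2 flow chart. Day-counting rule from SAP 5.4.2 and 6.1. Full adherence and no visit-window extension are assumed first.

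**Group 2, planned schedule**

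| Drug | SAP formula, literal | Scheduled intake | Difference |
|---|---|---|---|
| Nintedanib, Days 9–16 | 8 × 300 = 2400 mg | 7 × 300 + 150 = 2250 mg | +150 mg; 150/2250 = +6.7% |
| Pirfenidone 801 mg, Days 1–16 | 16 × 2403 = 38448 mg | 15 × 2403 + 801 = 36846 mg | +1602 mg; 1602/36846 = +4.3% |

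In capsules, the compliance denominator with its part-day footnote is 7 × 2 + 1 = 15 nintedanib and 15 × 9 + 3 = 138 pirfenidone. The total-dose formula implies 2400/150 = 16 and 38448/267 = 144.

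**Visit windows.** The absolute offset stays the same and the percentage shrinks.
- Nintedanib, combination phase 3 days longer: 11 × 300 = 3300 against 3150 mg (+4.8%).
- Pirfenidone over 19 days: 45657 against 44055 mg (+3.6%).
- Pirfenidone over 22 days: 52866 against 51264 mg (+3.1%).

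**Reduced pirfenidone dose.** Assuming 534 mg at every intake including Day 16: 16 × 1602 = 25632 against 15 × 1602 + 534 = 24564 mg (+1068 mg, +4.3%).

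**Group 1 pirfenidone.** Every planned day is a full tid day; Protocol 10.2 has the remaining Day 2 doses and the Day 23 evening dose taken at home. The formula gives 7 × 801 + 7 × 1602 + 8 × 2403 = 36045 mg, which equals the schedule.

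**One missed intake on a treated day** (assumed for illustration)
- Group 2 nintedanib: 2400/(2250 − 150) = +14.3%.
- Group 2 pirfenidone at 801 mg: 38448/(36846 − 801) = +6.7%.
- Group 1 pirfenidone, one 801 mg intake: 36045/(36045 − 801) = +2.3%.

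**Group 1 nintedanib.** The amount given is 2 × 150 = 300 mg, but 5.4.2 has no matching level. Forcing the bid level gives 2 × 300 = 600 mg if two days are counted, or 23 × 300 = 6900 mg if the span from Day 1 to Day 23 is used.

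**The case against.** The strongest answer is that *actual dose* is not defined. An analyst could enter Day 16 at the dose really given, in which case the Group 2 totals are exact. The once-daily nintedanib level in 5.4.3 shows that the authors had single-dose days in mind. This stands as a possibility, and it makes the overstatement conditional on the literal reading. It does not remove the point: 5.4.2 lists only bid and tid levels, omits the part-day footnote, and neither section has a single-intake level for pirfenidone.

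Several stronger readings are tempting but not supported:

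- *All completers are affected.* The Group 1 pirfenidone total is exact under full adherence.
- *Missed dosing is ignored.* Interruptions are removed from on-treatment time by SAP 6.1, and compliance counts capsules taken. Only isolated missed intakes on a treated day remain in the total.
- *The formula might understate dose because the level is per intake.* SAP 5.4.2 states doses as bid or tid regimens multiplied by days, and 5.4.3 converts the same regimens to capsules per day. A per-intake reading is strained.
- *Errors near 30% are to be expected, because 80% compliance is acceptable.* In Protocol 4.3 the 80–120% range triggers counselling and a diary check. For nintedanib, 80% would mean missing 3 of 15 intakes, which is hard to square with the seven consecutive days required before Visit 3b.
- *The exposure and compliance tables would visibly contradict each other.* One is in mg and the other in percent; a fully adherent patient shows 100% compliance under either definition of total dose. The conflict lies in the derivations.

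**Conclusion.** The point holds in a limited form. Taken literally, SAP 5.4.2 overstates total dose for a fully adherent Group 2 completer on the planned schedule by 150 mg nintedanib (+6.7%) and, at 801 mg tid, by 1602 mg pirfenidone (+4.3%). Any isolated missed intake adds to that. These sizes assume that Day 16 is credited as a full bid or tid day, which the listed levels suggest but the SAP does not state outright.

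The consequence is minor. Total dose appears only in descriptive tables, and the Group 2 offset is nearly constant across completers. A reader should not infer any effect on the PK endpoints, the PK analysis set, the ANOVA or the sample size, because none of them uses this quantity.

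**What to change.** Replace the total-dose line in SAP 5.4.2 with: number of capsules actually taken (the numerator already used in 5.4.3) times capsule strength, 150 mg for nintedanib and 267 mg for pirfenidone, summed over the treatment period.

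State that each dose given in the clinic is counted exactly once. This matters because Protocol 4.1.4 has patients bring their own medication to the PK visits, and the documents do not say whether capsules swallowed there are already in the count; simply adding clinic doses could count them twice.

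This handles the Day 16 part-day and missed intakes, and it gives Group 1 nintedanib a defined total of 300 mg. Carrying the 5.4.3 footnote into 5.4.2 would be a smaller change, but it would settle only the part-day.

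The cost is one SAP line and a small programming change. Capsule counts (Protocol 4.3), diary entries (5.3.6) and clinic intake times (5.4.1) are already collected.

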5.4.3 Treatment compliance

Compliance for nintedanib (group 2 only) and compliance for pirfenidone will be calculated separately over the study as:

$$\text{Compliance [\%]} = \frac{\text{Number of capsules actually taken over the period}}{\text{Number of capsules which should have been taken over the period}} \times 100$$

The number of capsules which should have been taken over the period will be calculated as:

Number of capsules which should have been taken over the period [capsules] = (date of last administration – date of first administration + 1) [days] × (number of capsules which should be taken per day) ^[1]

^[1] The time of first/ last administration are taken into account, so fewer capsules may be expected to be taken on some days.

For nintedanib, the number of capsules which should be taken per day at dose 150 mg qd is 1. The number of capsules which should be taken per day at dose 150 mg bid is 2.

For pirfenidone, the number of capsules which should be taken per day is 3 at dose 267 mg tid, 6 at dose 534 mg tid, and 9 at dose 801 mg tid.

Only treatment interruptions not due to AE will be considered a compliance issue and will be taken into account in the calculation (duration of interruptions due to AE will be subtracted from the duration of the study period).

Compliance will be categorised as follow: <50%, >=50% to <80%, >=80% to <= 120%, > 120%.

5.4.4 Liver enzyme and bilirubin elevations

Liver enzyme and bilirubin elevations will be reported using the two following definitions:

- (ALT \geq 3xULN and/or AST \geq 3xULN) AND bilirubin \geq 2xULN (1)
- ALT \geq 5xULN and/or AST \geq 5xULN

These elevations are defined within a time window of 30 days i.e. the elevation of bilirubin should appear within 30 days of the elevation of AST and/or ALT. Potential Hy's law cases, using the definition (1) above, will be presented using graphs.

Depending on the number of patients experiencing liver enzyme elevations, other cut-offs may be considered.

Maximum individual elevations based on worst value on treatment will be defined as:

- ≥ 3 *ULN; ≥ 5 *ULN; ≥ 8 *ULN for AST and ALT
- ≥ 1.5 *ULN; ≥ 2 *ULN for Bilirubin
- ≥ 1.5 *ULN; ≥ 2 *ULN for alkaline phosphatase
- ≥ 1 *ULN; ≥ 3 *ULN for Gamma-Glutamyl-Transferase

6. GENERAL ANALYSIS DEFINITIONS

6.1 TREATMENTS

For treatment specifications, see Section 4 of CTP.

The following trial periods will be defined: screening, post-entry, treatment period, off-treatment, Residual Effect Period, follow-up and post-study as follows:

Note: the last day of each of the following periods is excluded.

- **Screening:** from informed consent to date of entry
- **Post-entry** (if applicable): from entry to first trial drug intake.
- **Treatment period:** from first trial drug intake (or re-start of treatment if interruption) to last trial drug intake (or the day before start date of interruption, if interruption) plus one day
- **Off-treatment** (if applicable): from start date of interruption to re-start of treatment
- **Residual Effect Period:** from the last trial drug intake plus one day to last trial drug intake plus 28 days plus one day.
- **Follow-up** (if applicable): from last trial drug intake plus 29 days up to the beginning of post-study period. This period is only created if last trial drug intake took place more than 28 days before trial completion (i.e. date of the follow-up visit or date where the patient discontinued prematurely the trial).
- **Post-study:** from the latest of last trial drug intake plus 29 days or date of trial completion plus 1 day to database lock

For safety analyses, data up to 28 days after last trial drug intake (inclusive) will be considered on-treatment.

